2.9 Rationale for pediatric dosing

(per [name], Chief Medical Officer, APT Pharmaceuticals)

The main safety concerns in this age group are to ensure that there is not excessive systemic exposure to cyclosporine and there is no impact on lung function. It is normal practice to dose the currently licensed forms of cyclosporine (eg Neoral) on the basis of weight and monitor blood levels of cyclosporine. In addition, data from Chua et al, 1994 in 8 children (median age 10.8 y) with cystic fibrosis showed that in this age group, age was not a factor in the amount of drug deposited following aerosol delivery. Therefore, it is proposed to use weight as the main determinant of dose and divide the pediatric population into two groups on the basis of weight. Current experience in the adult population indicates that six adult subjects weighing less than 45 Kg (range 34.5 - 44.3 Kg) have been exposed to CIS. All six achieved a dose of 300 mg in the titration phase and none have reported

adverse events associated with study drug. The lightest subject had a peak serum cyclosporine level of 39.7 ng/mL one hour after the inhalation. This level is substantially below the therapeutic level set for systemic therapy (250 -350 ng/mL), suggesting that systemic exposure is not likely to be dose limiting at least in children above 35 kg.

Since the same nebulizer/compressor system will be used in the pediatric population, the proportion of nominal dose which is emitted at the mouth-piece will remain constant. The lung delivered dose is then dependent upon minute ventilation (slightly lower than adults across this age group) and air entrainment (less dilution of the dose due to a lower inspiratory flow rate in children) these factors will exist as a continuum across the population having a greater impact in the smaller younger subjects. Although the adult data suggests that there is a wide therapeutic margin (very low systemic cyclosporine exposure) it would seem prudent to reduce the nominal dose in the youngest, lightest population. The proposed dose for the pediatric age group is as follows:

Weight \geq 35 Kg dose at 300 mg
Weight < 35 Kg dose at 200 mg

This dosing schedule is being used in a multicenter phase III Trial, NCT00755781.

2.10 Clinical and Scientific Justification

Because patients who are eligible for this trial have already demonstrated a clinical response to CIS, continuation of therapy is warranted. Therefore, we propose this extended access phase II clinical trial designed to evaluate the safety and efficacy of long term use of inhaled cyclosporine in lung transplant and hematopoietic transplant recipients.

This study also seeks to further define the inflammatory pathways associated with BOS in stem cell transplant and lung transplant recipients and to investigate and compare similarities and differences in the pathogenesis of BOS following long-term therapy. Bronchoalveolar lavage will be studied using multiplex cytokine arrays, flow cytometry, and gene expression profiling. These studies will be performed on samples collected from patients and will promote further delineation of the underlying pathogenesis in BOS. Additionally, this study will examine the anti-inflammatory effects of cyclosporine on mediators of inflammation and differential gene expression in these populations. This has not been thoroughly studied in hematopoietic stem cell transplant recipients. This study evaluating the long term safety and efficacy of aerosolized cyclosporine will contribute to a greater understanding of the pathogenesis of bronchiolitis obliterans, and set the stage for larger trials in hematopoietic stem cell transplant and lung transplant recipients.

3.0 INVESTIGATIONAL PRODUCT

Please refer to the Investigator's brochure for Cyclosporine Inhalation Solution (CIS).

4.0 STUDY DESIGN

The study is designed as extended access study following response to initial treatment on the companion non-randomized, Phase II study of aerosolized cyclosporine A in solution with propylene glycol (CIS) in hematopoietic stem cell transplant recipients or lung transplant recipients who have been diagnosed with biopsy proven bronchiolitis obliterans or Bronchiolitis Obliterans Syndrome. As of March 2017 this study is no longer enrolling lung transplant recipients.

11-H-0064 Am L

Version Date: 10 May 2019

PI: [name]

[figure not shown]
Week 18

11-H-0064 Am L

Version Date: 10 May 2019

PI: [name]

Maximum of 39
PBSCT and 39 lung
transplant pt who
have completed
10-H-0196

	Baseline	Wk 24	Wk 30	Wk 36	Wk 42	Wk 48	Wk 54	Wk 60	Wk 70	After Wk 70	
(week 18 assessment)											
PFTs		PFTs	PFTs	PFTs	PFTs	PFTs	PFTs	PFTs	PFTs	PFTs	
Labs		Labs	Labs	Labs	Labs	Labs	Labs	Labs	Labs	(BAL and CT if indicated)	
BAL			BAL		BAL		BAL		BAL		
QOL			CT		CT		CT		QOL		
CT			Progression* FEV1≥20% decline, worsening status,							CT	

* Based on two successive measures at least two weeks apart

5.0 ELIGIBILITY ASSESSMENT

5.1 Inclusion criteria

- 5.1.1** Completed the End of Study visit (week19) on the initial protocol (Phase II Trial of Cyclosporine Inhalation Solution (CIS) in Lung Transplant and Hematopoietic Stem Cell Transplant Recipients for Treatment of Bronchiolitis Obliterans) in the preceding twelve weeks.
- 5.1.2** Patients have shown evidence for a clinical benefit to CIS as evidenced by one or more of the following:
 - 5.1.2.1** Improvement in pulmonary function defined by a 10% or more increase in the FEV₁ at week 18, confirmed with repeat PFTs at least 1 week apart.
 - 5.1.2.2** In patients with progressive disease at study entry on the initial protocol (Phase II Trial of Cyclosporine Inhalation Solution (CIS) in Lung Transplant and Hematopoietic Stem Cell Transplant Recipients for Treatment of Bronchiolitis Obliterans), stabilization in pulmonary function, defined as less than a 10% improvement in FEV₁ or less than 10% decline in FEV₁ at week 18, confirmed with repeat PFTs at least 1 week apart.
 - 5.1.2.3** In patients with stable disease (active BOS stable by FEV₁ criteria) at study entry on the initial protocol (Phase II Trial of Cyclosporine Inhalation Solution (CIS) in Lung Transplant and Hematopoietic Stem Cell Transplant Recipients for Treatment of Bronchiolitis Obliterans), stabilization in pulmonary function, defined as less than a 10% improvement in their FEV₁ or less than 10% decline in FEV₁, and a decrease in the dose of one or more systemic immunosuppressants by at least 20% *(sustained for 3 weeks, excluding adjustments made for target drug levels)
* The criteria for study entry on this extension protocol are not the same as the criteria for response on the primary protocol to allow for entry of patients on this extension protocol, which is deriving some clinical benefit, but have not met the full response criteria as defined in the primary protocol.

5.2 Exclusion criteria

- 5.2.1** More than a twelve week gap in study drug administration (CIS)
- 5.2.2** Evidence of uncontrolled, pulmonary infection
- 5.2.3** ECOG performance status greater than or equal to 3
- 5.2.4** Patient pregnant or breast feeding or not willing to continue the use of an approved method of birth control
- 5.2.5** Life expectancy less than 18 weeks
- 5.2.6** History of hypersensitivity reaction to propylene glycol
- 5.2.7** Documented allergy or intolerance to CIS

- 5.2.8** History of untreated coronary insufficiency, severe cardiac arrhythmias, and/or uncontrolled hypertension.
- 5.2.9** Serum creatinine >2.5 mg/dl
- 5.2.10** Inability to comprehend the investigational nature of the study and provide informed consent

6.0 TREATMENT PLAN

6.1 Pre-treatment Medication (albuterol)

Subjects will receive metered dose inhaler albuterol, 2 puffs as needed for prevention of bronchospasm or 3 ml solution for nebulization. Patients may receive levalbuterol in place of albuterol or not receive pre-treatment.

6.1.1 Inhalation device: Subjects will be instructed regarding the use of the inhalation device as follows:

- Shake the inhaler well.
- Breathe out as completely as possible through your mouth.
- Hold the canister with the mouthpiece on the bottom, facing you and the canister pointing upward. Place the open end of the mouthpiece into your mouth. Close your lips tightly around the mouthpiece.
- Breathe in slowly and deeply through the mouthpiece. At the same time, press down once on the container to spray the medication into your mouth.
- Try to hold your breath for 10 seconds, remove the inhaler, and breathe out slowly.
- Wait 10 minutes before beginning cyclosporine nebulizer treatment.

6.1.2 Nebulizer: Subjects will be instructed regarding the use of the nebulizer device as follows:

- Before treatment, wash your hands with soap and water and dry completely.
- Place the air compressor on a sturdy surface that will support its weight. Plug the cord from the compressor into a properly grounded (three-prong) electrical outlet.
- Carefully measure medications exactly as you have been instructed and put them into the nebulizer cup.
- Assemble the nebulizer cup and mask or mouthpiece.
- Connect the tubing to both the aerosol compressor and nebulizer cup (with filter if beginning treatment with cyclosporine).
- Turn on the compressor to make sure it is working correctly. You should see a light mist coming from the back of the tube opposite the mouthpiece.
- Sit up straight on a comfortable chair. If the treatment is for your child, he or she may sit on your lap. If you are using a mask, position it comfortably and securely on you or your child's face. If you are using a mouthpiece, place it between you or your child's teeth and seal the lips around it.
- Take slow, deep breaths.
- Continue the treatment until the medication is gone (an average of 10 minutes for albuterol). The nebulizer will make a sputtering noise, and the cup will have just a little medication remaining.

- If dizziness or jitteriness occurs, stop the treatment and rest for about 5 minutes. Continue the treatment, and try to breathe more slowly. If dizziness or jitteriness continues to be a problem with future treatments, inform your doctor.
- During the treatment, if the medication sticks to the sides of the nebulizer cup, you may shake the cup to loosen the droplets.
- After each treatment, rinse the nebulizer cup thoroughly with warm water, shake off excess water, and let air dry.
- Wait 10 minutes before beginning cyclosporine nebulizer treatment.

6.1.3 Concomitant Medications of Concern with albuterol (concurrent use will be per PI discretion and carefully monitored) Subjects will be queried as to what prescription medications, vitamins, nutritional supplements, and herbal products they are taking, or have stopped taking within the past two weeks as medication dose adjustments may be required or subjects carefully monitored for side effects with the following medications:

- beta blockers such as atenolol (Tenormin), labetalol (Normodyne), metoprolol (Lopressor, Toprol XL), nadolol (Corgard), and propranolol (Inderal); digoxin (Lanoxin); diuretics; epinephrine (Epipen, Primatene Mist); other inhaled medications used to relax the air passages such as metaproterenol (Alupent) and levalbuterol (Xoponex); and medications for colds
- antidepressants such as amitriptyline (Elavil), amoxapine (Asendin), clomipramine (Anafranil), desipramine (Norpramin), doxepin (Adapin, Sinequan), imipramine (Tofranil), nortriptyline (Aventyl, Pamelor), protriptyline (Vivactil), and trimipramine (Surmontil); and monoamine oxidase (MAO) inhibitors, including isocarboxazid (Marplan), phenelzine (Nardil), selegiline (Eldepryl, Emsam), and tranylcypromine (Parnate).

6.1.4 Subjects will also be instructed to discontinue albuterol and notify the research team immediately if they:

- Become pregnant, plan to become pregnant, or are breast-feeding.
- Experience severe wheezing and difficulty breathing immediately after it is inhaled.

6.1.5 Subjects will be instructed not to administer the albuterol and /or study drug on the day of assessments, as the albuterol and/or CsA may complicate the interpretation of the pulmonary function testing.

6.2 Study Drug (Aerosolized Cyclosporine A in solution with Propylene glycol) Administration

6.2.1 Treatment plan:

Subjects will continue self administration of aerosolized cyclosporine A in solution with propylene glycol using a Sidestream nebulizer with the Invacare Mobilair compressor at 30 psi at the maximum tolerated dose established during participation on the initial protocol (Phase II Trial of Cyclosporine Inhalation Solution (CIS) in Lung Transplant and Hematopoietic Stem Cell Transplant Recipients for Treatment of Bronchiolitis Obliterans), 3 times weekly (150 mg to 300 mg inhalation dose, total volume 2.4 to 4.8 ml). Continued dosing will be dependent on response and tolerance.

Hematopoietic stem cell transplants (Group A)

1. Any patient that has continued improvement in lung function, as defined by 10% or more increase in FEV₁, as compared to their new baseline FEV₁ value, determined by average of week 18 and 19 PFT assessments on the initial study (Phase II Trial of Cyclosporine Inhalation Solution (CIS) in Lung Transplant and Hematopoietic Stem Cell Transplant Recipients for Treatment of Bronchiolitis Obliterans), and/or continued success with weaning systemic immunosuppressants will be maintained on CIS with no effort to taper CIS.
2. Patients who show stabilization in PFTs for 6 months, as defined by less than 10% increase in FEV₁ or less than 10% decline in FEV₁, as compared to their new baseline FEV₁ value, determined by average of week 18 and 19 PFT assessments on initial treatment study (Phase II Trial of Cyclosporine Inhalation Solution (CIS) in Lung Transplant and Hematopoietic Stem Cell Transplant Recipients for Treatment of Bronchiolitis Obliterans), that are either off systemic immunosuppressants or cannot have further tapering of their systemic immunosuppressants, may undergo tapering of CIS, at the discretion of the PI.
 - a. Patients successfully tapered off CIS will continue to have clinical assessments and PFTs performed at 6 week intervals and will be taken off study should PFTs remain stable (in the absence of a need for increased systemic immunosuppression for BO/BOS) for a period of 12 months off therapy.
 - b. Patients who have worsening of BO/BOS associated with tapering CIS will have the CIS reinitiated at the patient's previously defined maximal tolerated dose.
3. Any subject that demonstrates disease progression, as defined by a 20% or more decline in FEV₁ on two successive measurements at least 3 weeks apart, or those who require an increase in the existing dose of one or more immunosuppressive therapies by at least 25% (sustained for 3 weeks, excluding adjustments made for target drug levels) above baseline levels from the primary protocol or the addition of new immunosuppressive therapies (sustained for 3 weeks) due to worsening symptoms related to BO/BOS, will be categorized as a treatment failure and will discontinue study drug administration and proceed with end of study drug assessment.

Lung transplant recipients (Group B) (No longer enrolling)

1. Any patient that has improvement or stabilization of lung function, as measured by PFTs will remain on CIS with no attempts to taper CIS.
2. Any subject that demonstrates disease progression, as defined by a 20% or more decline in FEV₁ on two successive measurements at least 3 weeks apart, or those who require an increase in the existing dose of one or more immunosuppressive therapies by at least 25% (sustained for 3 weeks, excluding adjustments made for target drug levels) above baseline levels from the primary protocol or the addition of new immunosuppressive therapies due to worsening symptoms related to BO/BOS, will be categorized as a treatment failure and will discontinue study drug administration and proceed with end of study drug assessment.

Deviation plan for a missed dose: Subjects will be treated with CIS three times weekly ideally on Monday, Wednesday, and Friday of the week. Should a subject miss a scheduled dose of CIS, we will attempt to alter the dosing regimen for that week so that the subject will still receive three doses of CIS over a week with a limit of 1 dose per day. Data will be captured and reported for subjects who deviate from the treatment plan.

Medication Holds: During study participation, subjects may be instructed to hold administration of CIS for development of an adverse event or other reason at the discretion of the PI. Information pertaining to the reason for and the duration of the medication hold will be captured in the patient's

medical record. If study drug is held for more than 7 days, the time of the hold will not be counted towards the overall study week count. Study drug can be held for up to 12 months.

6.2.2 Special Instructions Regarding the Administration of Aerosolized Cyclosporine A

Patients will follow nebulizer instructions (section 6.1.2) with the following instructions specific to CsA: Continue the treatment until the medication is gone (approx. 10-30 minutes for cyclosporine).

A new nebulizer should be used after albuterol administration. Aerosolized CsA is provided in single use vials. Any CsA remaining in the vial after administration should be discarded immediately.

Subjects will be given a medication log and asked to record their CIS administration on the log. Subjects will be encouraged to capture this information, but failure to comply with this request will not be reported as a protocol deviation.

6.2.3 Permitted Concomitant Medications

Post Transplant Medications:

Subjects that require an increase in the existing dose of one or more immunosuppressive therapies by at least 25% above baseline levels from the primary protocol due to worsening BOS symptoms (sustained for 3 weeks, excluding adjustments made for target drug levels) or the addition of new immunosuppressive therapies (sustained for 3 weeks) due to worsening symptoms related to BO/BOS, will be considered treatment failures. However, if the increase or addition of new immunosuppressive therapies is for GVHD not involving the lung or is to maintain baseline drug levels, this data will be captured and the patient will continue on study. Efforts will be made to make no changes in existing medical therapies other than tapering immunosuppressants in patients who have PFTs showing stable or improved pulmonary function. Again, this data will be captured.

Lung Infection Prophylaxis:

Lung infection prophylaxis will be at the discretion of the PI, taking into account the patient's other concomitant medications and medical history. The following are guidelines:

- For PCP pneumonia prophylaxis, subjects will take Bactrim, one double strength tablet (800/160mg) orally three times weekly or aerosolized pentamidine 300mg every four weeks by inhalation.
- For antiviral prophylaxis, subjects will receive acyclovir 800 mg twice daily Pediatric patients less than 40kgs will receive acyclovir 20mg/kg po twice daily to a maximum dose of 800mg twice daily.
- For antibacterial prophylaxis, subjects will receive penicillin 500mg twice daily or for penicillin allergic patients, azithromycin 250mg daily.
- Subjects who are already on adequate, alternative prophylaxis agents prescribed by their primary transplant teams can remain on their prior regimens.

6.2.4 Concomitant Medications of Concern with CsA (concurrent use will be per PI discretion and carefully monitored)

- Due to potential for drug interactions, other short acting sympathomimetic aerosolized bronchodilators, beta-adrenergic receptor blocking agents, digoxin, monoamine oxidase inhibitors or tricyclic antidepressants will be allowed per PI discretion.
- Due to the potential for compromising the primary endpoint, subjects requiring an increase in systemic immunosuppression or who initiate new immunosuppressive agents, such as oral tacrolimus, CSA, prednisone, mycophenolate mofetil (MMF) or azathioprine due to symptoms of GVHD *not* involving the lung, will remain on study and will have concurrent use of these medications carefully tracked and accounted for during and at the end of study data analysis.
- Cyclosporine can interfere with or be affected by multiple drugs due to its metabolism through the CYP3A4 enzyme. As such, patients who are taking medications which, are either substrates for, inducers of, or inhibitors of CYP3A4 (i.e. oral cyclosporine) will be closely monitored (see appendix c).

7.0 CLINICAL MONITORING PLAN

Human Biologic materials will be collected as follows for the clinical evaluation and management of the patient. Samples will be ordered and tracked through the CRIS screens. Should a CRIS screen not be available, the NIH form 2803-1 will be completed and will accompany the specimen and be filed in the medical record.

7.1 On study assessments: Subjects will be asked to return to the NIH Clinical Center the end of Week 24, 30, 36, 42, 48, 54, 60 (+/- 7 days) for the following assessments:

- Interim assessment with emphasis on symptomatology
- Vital signs
- ECOG performance status
- Review of concomitant medications and adherence
- CBC with differential (when possible, done concurrently with post transplant monitoring)
- Acute Care, Mineral and Hepatic Panels (when possible done concurrently with post transplant monitoring)
- Plasma cyclosporine level
- Peripheral blood samples
- Repeat Serum Beta- HCG in women of childbearing potential
- Pulmonary Function tests
 - Forced Spirometry
 - Slow Spirometry
 - Lung volumes with nitrogen washout
 - Single Breath Diffusion
 - Six minute walk test
 - Exhaled Nitric Oxide measurement (in a subset of subjects)
 - Review of Peak Flow measurements
- Bronchoscopy and bronchoalveolar lavage (BAL) (Weeks 30, 42, 54 only)*
BAL to be analyzed by
 - Luminex cytokine arrays
 - Flow Cytometry
 - Gene expression profiles

- Proliferative, cytotoxic, and apoptotic response of BAL lymphocytes to 3rd party epithelial cells and allogeneic lymphocyte population
- T regulatory cell quantification by real time PCR
- High Resolution Chest CT (weeks 30, 42, 54 only)*

* Bronchoscopy and High-resolution CT scans are optional unless clinically indicated.

7.2 End of week 70 and end of study assessments

Patients will be monitored at week 70 (+/- 1 week) and at end of study participation with the following assessments:

- Assessment with emphasis on symptomatology
- Vital signs
- ECOG performance status
- Review of concomitant medications and compliance
- CBC with differential (if possible, done concurrent with post transplant monitoring)
- Acute Care, Mineral and Hepatic Panels (if possible, done concurrently with post transplant monitoring)
- Plasma cyclosporine level
- Repeat Serum Beta- HCG in women of childbearing potential
- Pulmonary Function tests
 - Forced Spirometry
 - Slow Spirometry
 - Lung volumes with nitrogen washout
 - Single Breath Diffusion
 - Six minute walk test
 - Exhaled Nitric Oxide measurement (in a subset of subjects)
 - Review Peak Flow measurements
- Bronchoscopy and bronchoalveolar lavage (BAL)*
 - Luminex cytokine arrays
 - Flow Cytometry
 - Gene expression profiles
 - Proliferative, cytotoxic, and apoptotic response of BAL lymphocytes to 3rd party epithelial cells and allogeneic lymphocyte population
 - T regulatory cell quantification by real time PCR using primers to fox p3
- Peripheral blood samples
- High Resolution Chest CT*
- Quality of life assessments
 - SF36
 - GVHD questionnaire (PBST transplant patients only)
 - HAP Questionnaire
 - CRQ-SAS questionnaire
 - Comfort of study drug administration

* Bronchoscopy and High-resolution CT scans are optional unless clinically indicated.

7.3 Long term follow up after Week 70 until withdrawal from study

After Week 70 assessments are completed, patients will return to the NIH Clinical Center every 6-12 weeks for routine assessment, physical exam and PFTs. Chest CTs, bronchoscopies and BALs will only be done as clinically indicated. The study drug will be made available until it is

commercially available, or until the pharmaceutical company (APT Pharmaceuticals) withdraws the NDA, or for six months if APT Pharmaceuticals undergoes a change of control.

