10.3 Data Analyses

Any patient who receives any amount of study medication during this extension study will be considered evaluable for safety analysis. Adverse events will be tabulated by severity and disease (lung versus hematopoietic).

Final statistical analysis of efficacy will be performed once all subjects have completed the end of study assessments and all data have been archived for analysis. We will use stratified analyses to account for effects of systemic immunosuppressive agents and other prognostic factors.

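### After week 70, 7.3 schedules no safety labs before the end-of-participation visit, and the adverse-event table in 10.3 cannot show late toxicity or allow for unequal exposure and time off drug

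*Combined protocol and SAP*

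**What the plan says.** **Visits.** Section 7.1 lists a blood count, acute care, mineral and hepatic panels, plasma cyclosporine and beta-HCG at weeks 24, 30, 36, 42, 48, 54 and 60. Section 7.2 repeats them: "Patients will be monitored at week 70 (+/- 1 week) and at end of study participation with the following assessments". For the time between week 70 and the end of participation, 7.3 says "patients will return to the NIH Clinical Center every 6-12 weeks for routine assessment, physical exam and PFTs". It makes CT, bronchoscopy and BAL conditional on clinical indication and does not mention laboratory tests.

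**Duration.** In 7.3, "The study drug will be made available until it is" on the market, the NDA is withdrawn, or six months have passed after a change of control at the manufacturer. No week is fixed.

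**Time off drug.** Section 6.2.1 states "Study drug can be held for up to 12 months", and holds over 7 days do not count toward the study week. Group A patients tapered off CIS are followed "for a period of 12 months off therapy" if they stay stable. Under 10.5.1 a patient may stop the drug and remain on study.

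**Analysis.** Section 10.3 says "Any patient who receives any amount of study medication during this extension study will be considered evaluable for safety analysis" and "Adverse events will be tabulated by severity and disease (lung versus hematopoietic". It names no period, person-time or on-drug/off-drug distinction. Its stratified analyses belong to efficacy. The stopping rule in 10.4 covers weeks 18-70 only.

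**The concern.** Long-term safety is part of the primary objective (1.1, 10.1). The quantified earlier safety experience with CIS (2.6.4, 13.3.1) comes from lung recipients. The Precis says inhaled cyclosporine had not been studied for BO after stem cell transplantation, and that is the only group enrolled after March 2017.

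Two gaps meet here. Progression to a grade 3 or 4 laboratory toxicity is a collected safety outcome (12.3), but only a drawn sample can reveal it, and after week 70 no draw is scheduled until the last visit. The one table named for safety also gives counts over follow-up of very different lengths, part of it off drug, with nothing to separate early from late. Followed as written, 10.3 would answer the long-term half of the safety question poorly.

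**Working it through.** **The plan's own safety figure.** The only computed one is the stopping rule in 10.4. An exact recursion over 39 subjects against the printed boundary gives stopping probabilities of 2.5, 19.5, 50.5, 77.9 and 98.2% at true rates of 5, 10, 15, 20 and 30%. The plan prints 2.2, 20.2, 51.5, 77.4 and 98.1%, so they agree within about one percentage point. The rule is not in dispute, but it does not reach past week 70.

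**Scheduled laboratory visits to week 70.** Seven from 7.1 plus week 70 from 7.2 make 8. Nominal gaps from week 18 are 6 weeks seven times, then 10. With one week of window at each end they are 6 + 2 = 8 and 10 + 2 = 12. These are study weeks. A hold over 7 days stops the clock, so calendar gaps can be much longer, and 7.4 allows 24-week spacing for long-distance patients. Testing before week 70 is scheduled, but not uniformly regular.

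**Scheduled visits after week 70.** For an end visit T weeks after week 70 and spacing s, the visits strictly in between number ceil(T/s) - 1. T is assumed, because the documents do not give it.

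| T (assumed) | s = 6 | s = 12 | s = 24 (7.4) |
|---|---|---|---|
| 52 weeks | 8 | 4 | 2 |
| 104 weeks | 17 | 8 | 4 |
| 156 weeks | 25 | 12 | 6 |

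The laboratory set is listed at none of these visits.

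**Why crude counts fall short (illustration only).** Assume a constant hazard giving 10% over the 52 weeks from 18 to 70, which is the 10.4 benchmark, and no dropout. The proportion with an event after T total weeks is 1 - 0.9^(T/52): 10.0% at 52 weeks, 14.6% at 78, 19.0% at 104, 27.1% at 156 and 34.4% at 208. The rate stays at -ln(0.9) = 0.105 per 52 weeks, or 10.5 per 100 person-years. The crude proportion more than triples through duration alone.

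Person-time without a period split is not enough either. If the hazard doubled after week 70, the late rate would be 21.1 per 100 person-years. The pooled rate, 10.54 x (52 + 2L)/(52 + L), would be 15.8 for L = 52 late weeks and 17.6 for L = 104.

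**What the recorded data allow.** Section 6.2.1 says that "the duration of the medication hold will be captured" in the medical record. Section 11.1 imports NIH laboratory data electronically and enters home-physician values. Section 12.3 collects adverse events and grade 3/4 laboratory progression, except those attributed to the transplant, post-transplant drugs or baseline disease. A split table can therefore be built, with an attribution-filtered laboratory numerator.

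**The case against.** A reader might infer that laboratory monitoring stops at week 70. The documents do not say so. The routine assessment in 7.3 is undefined and may include blood tests. Section 2.8 promises close monitoring of cyclosporine levels in children, and 6.2.4 of patients on CYP3A4-interacting drugs. Section 7.4 allows home laboratory data, and 13.4.1 ties clinical sampling to routine post-transplant care. Clinical toxicity can be picked up at the 6-12-weekly visits (12.1), the DSMB evaluates all serious events (10.4), and a persistent abnormality could appear at the final visit. All of this stands and narrows the gap to asymptomatic or transient laboratory change. It does not close it, because none of these provisions sets an interval.

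It can also be said that 10.3 nowhere states that early and late data are pooled, and that nothing forbids extra columns. That is true. But the table as specified has no time dimension, and whether to add one would be decided after the data are seen, on a primary objective.

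Finally, 13.4.1 says the study is in data and sample analysis only, so the visit schedule can no longer be changed for these patients. This is correct, and it moves the remedy to the analysis.

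**Conclusion.** The point holds for what is scheduled and what is tabulated, and it is worth acting on: 10.3 as written gives crude counts over unequal on-drug and off-drug time, and a better descriptive method is still available. Its size cannot be computed, since the documents give neither exposure nor laboratory testing after week 70. The visit counts and rates above rest on assumed durations and hazards.

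Three stronger readings are tempting and not supported:

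- That the table would show a falsely low late count. It has no period split, so it shows no late count at all.
- That follow-up after taper inflates apparent exposure by a stated factor. Section 10.3 has no exposure denominator to inflate.
- That upper bounds on a late event rate after zero events measure the weakness. They need a number tested that the documents do not give, and the 39 per group is a maximum, not the number who pass week 70.

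**What to change.** **In 10.3, now.**

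- Report adverse events, treatment-related serious adverse events and collected grade 3/4 laboratory events by group, separately for weeks 18-70 and after week 70, on the protocol's own study-week clock.
- Give approximate person-weeks on CIS for each period, excluding holds and time off drug. List events with onset off drug separately, so that numerator and denominator match.
- For laboratory data, give the number of subjects tested and the number of draws (NIH and home) in each period. Note the attribution exclusions of 12.3, and do not read the absence of late events as evidence of safety where no samples were drawn.
- Keep the split descriptive, because those who reach the late period are patients who had not failed or stopped. Leave the 10.4 boundary as it is.

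**Cost.** Chart abstraction for hold, taper and draw dates. Dosing logs are voluntary (6.2.2), so person-time will be approximate, and late cells will be small. No patient contact is needed.

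**In 7.3, only if dosing resumes or the schedule is reused.** List the 7.1 safety laboratory set at the existing post-week-70 visits while on CIS, drawn with post-transplant monitoring where possible. This costs extra routine draws and data entry and cannot help current subjects.
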